6.6 Pregnancy

Pregnancy is not regarded as an AE unless there is a suspicion that an investigational vaccine may have interfered with the effectiveness of a contraceptive medication. Any pregnancy that occurs in a study participant and during study participation must be reported using a clinical study pregnancy form. To ensure subject safety, each pregnancy must be reported to the sponsor within 2 weeks of learning of its occurrence. The pregnancy must be followed-up to determine outcome (including spontaneous miscarriage, elective termination, normal birth, or

congenital abnormality) and status of mother and child, even if the subject was discontinued from the study. Pregnancy complications and elective terminations for medical reasons must be reported as an AE or SAE. Spontaneous miscarriages must be reported as an SAE.

Any pregnancy, brought to the investigator's attention after the subject has completed the study, but occurring while the subject was in the study, must be promptly reported to the sponsor.

Pregnancy is an exclusion criterion, and a urine pregnancy test is required in sexually active heterosexual females a) at the time of enrolment; and b) on the day of and preceding any study vaccination.

7 Statistical and Analytical Plan

7.1 Sample Size Calculations

Approximately 360 subjects will be enrolled and randomly assigned (1:1:1) to 1 of 3 treatment groups (refer to Table 3-1) to contribute to safety and efficacy assessments. Enrolment will be operationally managed at the study level to maintain a minimum number of subjects enrolled in 2 age groups: 6 to 10 years, inclusive; and 11 to 17 years, inclusive. It is estimated that a 10% drop-out rate will occur, allowing for approximately 108 evaluable subjects per treatment group.

Primary immunogenicity endpoints: The sample size is based on calculations to achieve adequate response on Day 29 over baseline of mucosal S-IgA for WCE assay in the BPZE1 and BPZE1 + Boostrix groups. Assuming the GMT follows a log-normal distribution, by applying a natural logarithmic transformation of the GMT, a paired t-test will be used to test the difference of mucosal S-IgA against WCE at Day 29 compared with baseline (equivalent to natural logarithmic transformation of the GMFR). With an effective sample size of N=108 subjects per group, the study provides 95% power for detecting an effect size of 0.35 for each of the two primary comparisons with a two-sided significance level of 0.05. By multiplying the power for each of the two comparisons, the study provides an overall power of 90% (=95%*95%) for testing both primary comparisons. Factoring in an estimated 10% drop-out rate, each treatment group would include approximately 120 subjects for a total of approximately 360 subjects in the study.

Key secondary endpoints: To demonstrate non-interference of IgG serum responses for the Boostrix-containing antigens (diphtheria, tetanus) at Day 29 when BPZE1 is co-administered with Boostrix (BPZE1 + Boostrix vs Boostrix), the test for non-inferiority of BPZE1 + Boostrix to Boostrix for the proportion with titer ≥ 0.1 IU/mL (for diphtheria, tetanus) has power exceeding 92% with approximately N=120 subjects per treatment group, assuming a noninferiority margin of -0.1, one-sided significance level of 0.025, 10% drop-out rate and the proportion with titer ≥ 0.1 IU/mL for the Boostrix treatment being at least 0.95.

To demonstrate non-interference of IgG serum responses for the Boostrix-containing antigens (PT, FHA, PRN) at Day 29 when BPZE1 is co-administered with Boostrix (BPZE1 + Boostrix vs Boostrix), the tests for non-inferiority of BPZE1 + Boostrix to Boostrix for each of the three IgG parameters (PT/FHA/PRN) have power of 97%, 100%, and 88%,

respectively, for detecting between group differences as observed in study IB-200P, with approximately 120 subjects per treatment group, one-sided significance levels of 0.025, 10% drop-out rate and non-inferiority margin of -0.693.

7.2 Blinded Sample Size Recalculation

A blinded sample size recalculation may occur when immunogenicity data for approximately 40 to 60 subjects per group are available. The standard deviation of the Day 29 change from baseline of S-IgA for WCE of natural logarithmic transformed GMFR will be computed. The standard deviation of natural logarithmic transformed GMTs of the IgG serum responses for the Boostrix-containing antigens (PT, FHA, PRN) at Day 29 will also be computed.

Proportions with titer ≥ 0.1 IU/mL for the IgG serum responses for the Boostrix-containing antigens (diphtheria, tetanus) at Day 29 will be estimated.

The standard deviations and proportions with titer ≥ 0.1 IU/mL will be computed in the full dataset and not by treatment group to ensure that the blinding is maintained. The sample size will then be recalculated with the potential to adjust the sample size accordingly.

A small committee consisting of select ILiAD leadership and an independent blinded statistician will evaluate the need to change sample size. The independent blinded statistician will use the standard deviation values estimated from the full dataset to recalculate the sample size. In addition to these pooled standard deviation values, the committee will also assess data completeness for the primary endpoint and drop-out rate.

The committee will meet and document its decision in a memorandum. This memorandum will include the pooled standard deviations, the updated power/sample size computations, and the final decision regarding any change in sample size.

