All AEs will be collected following re-vaccination/attenuated challenge on Day 85 through Day 113. Following Day 113, only MAAEs, AESIs, and SAEs will be collected through Day 169/EOS.

Estimated Study Duration: Study duration is approximately 9 months and duration of subject participation is approximately 6 months.

Immunogenicity and Colonization Assessments:	Immune measurements will be conducted on serum (IgG and IgA) and nasal mucosal secretion (S-IgA) samples for anti-pertussis antibodies of WCE, PT, FHA, and PRN, as well as any additional antigens included in assay development. Serum bactericidal activity (or other functional assays identified) will be measured in a subset of subjects. Cellular-mediated responses to BPZE1 and Boostrix (Th1/Th17 vs Th2) will be assessed by ELISpot or flow cytometry in subjects at baseline and Day 8 (safety lead-in cohort) and Day 85 and Day 113 (subset of substudy subjects). Additional testing for antibodies specific to B. pertussis may be performed at a later date as BPZE1 induces broader immunity more similar to natural infection induced immunity and does not contain the purified antigen levels of PT, FHA, and PRN found in Boostrix. Mid-turbinate/nasopharyngeal samples will be evaluated by real-time PCR or by B. pertussis culture for colonization of B. pertussis . Subjects will consent for the use of samples for further anti-pertussis antibody testing or other assay development as part of the standard consenting process. Aliquots of collected samples from this study may be retained for additional testing of biological responses (eg, antibodies, T-cell responses, microbiome) specific to future development of BPZE1 and ILiAD Biotechnologies' B-Tech program for a maximum of 15 years (starting from the date at which the last subject had the last study visit), unless local rules, regulations, or guidelines require different time frames or different procedures, and in accordance with subject consent.
Safety Assessments:	Safety assessments for all subjects will include the following: vital sign measurements (including body temperature and heart rate), targeted physical examinations, reactogenicity, and AEs (including MAAEs, AESIs, and SAEs).

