5.2 Treatments Administered

Subjects in Treatment Group A (N ~120) will receive an intranasal application of 10^9 CFU BPZE1, with approximately 0.4 mL per nostril (0.8 mL total volume delivered); and an IM injection of 0.5 mL placebo (sterile normal saline for injection) to the deltoid region on Day 1. Intranasal application of BPZE1 or placebo should precede IM injection of Boostrix or placebo by at least 10 minutes (minimum of 30 minutes for subjects in the safety lead-in cohort of 11 to 17 year olds). For the safety lead-in cohort, a minimum of 30 minutes must occur between intranasal and IM vaccinations on Day 1.

Subjects in Treatment Group B (N ~120) will receive an intranasal application of 10^9 CFU BPZE1, with approximately 0.4 mL per nostril (0.8 mL total volume delivered); and an IM injection of 0.5 mL Boostrix (aP vaccine, manufactured by GlaxoSmithKline) to the deltoid region on Day 1. Intranasal application of BPZE1 or placebo should precede IM injection of Boostrix or placebo by at least 10 minutes (minimum of 30 minutes for subjects in the safety lead-in cohort of 11 to 17 year olds).

Subjects in Treatment Group C (N ~120) will receive an intranasal application of lyophilized buffer reconstituted in sterile water, with approximately 0.4 mL per nostril (0.8 mL total volume delivered); and an IM injection of 0.5 mL Boostrix (aP vaccine, manufactured by GlaxoSmithKline) to the deltoid region on Day 1. Intranasal application of BPZE1 or placebo should precede IM injection of Boostrix or placebo by at least 10 minutes (minimum of 30 minutes for subjects in the safety lead-in cohort of 11 to 17 year olds).

All subjects participating in the optional substudy will receive a second intranasal application of 10^9 CFU BPZE1, with approximately 0.4 mL per nostril (0.8 mL total volume delivered) on Day 85.

All subjects will be monitored for study vaccination-related events for at least 30 minutes following the last vaccination (eg, 30 minutes following IM vaccination).

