10.8 Publications

After completion of the study, the data may be considered for reporting at scientific meetings or for publication in scientific journals. In these cases, the sponsor will be responsible for these activities to determine how the manuscript is written and edited, the number and order of authors, the publication to which it will be submitted, and other related issues. The sponsor has final approval authority over all such issues.

Data are the property of the sponsor and cannot be published without prior authorization from the sponsor, but data and publication thereof will not be unduly withheld.

11 Study Management

The administrative structure will include an unblinded biostatistics team (statisticians and programmers) and an external SMC.

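### The optional blinded sample-size recalculation pools in the arm given no Boostrix, so its SDs and seroprotection proportions do not estimate what the BPZE1 + Boostrix versus Boostrix tests need.

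*Protocol*

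**What the plan says.** Protocol 7.2 makes the step optional: "A blinded sample size recalculation may occur when immunogenicity data for approximately 40 to 60 subjects per group are available". Three kinds of quantity are taken:

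- the SD of the Day 29 log change in S-IgA against WCE;
- the SDs of the Day 29 log IgG values for PT, FHA and PRN;
- the proportions at or above 0.1 "IU/mL for the IgG serum responses for the Boostrix-containing antigens (diphtheria, tetanus) at Day 29 will be estimated".

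The SDs and proportions "will be computed in the full dataset and not by treatment group to ensure that the blinding is maintained". Then: "The independent blinded statistician will use the standard deviation values estimated from the full dataset to recalculate the sample size". A small committee of sponsor leadership and that statistician decides on any change and records it in a memorandum. Section 7.2 states no formula, power target or cap.

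Protocol 7.1 and 7.4.2 and SAP 4.1.2 and 8.2 define the key secondary tests as Group B against Group C only. Protocol 5.2 gives Group A intranasal BPZE1 and "an IM injection of 0.5 mL placebo (sterile normal saline for injection) to the deltoid region on Day 1". The protocol synopsis (Immunogenicity and Colonization Assessments) says that BPZE1 "does not contain the purified antigen levels of PT, FHA, and PRN found in Boostrix". The SAP repeats the planning assumptions but does not describe the recalculation.

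**The concern.** Blinded pooling of the arms being compared is standard and nearly harmless, because it adds only their small expected difference to the SD. Here the pool also holds a third arm that is outside the comparison and differs by design in the injection that drives the endpoint. Group A gets no diphtheria or tetanus toxoid and none of Boostrix's purified pertussis antigens. Its separation from the other arms enters the SD as if it were within-arm spread, and it shifts the proportions.

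The memorandum's updated power figures could then be misread for the key secondary endpoints. An overstated need could add children aged 6 to 17 to a trial of a live investigational vaccine; an understated one could give false reassurance.

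**Working it through.** **Inputs.** From SAP Tables 4-1 and 4-2: 108 evaluable per arm; one-sided 0.025; margin −0.693 on the log scale for IgG and −0.1 for proportions. Planned difference and SD: PT −0.234 and 0.8759; FHA −0.019 and 0.8158; PRN −0.075 and 1.4363. Diphtheria/tetanus proportion 0.95 in both arms.

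**Assumed, because the documents do not say:** Group A's fold separation, its SD, its diphtheria/tetanus proportion, and a 90% power target for sample sizes.

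**Reproducing the plan.** For IgG, a non-central t with non-centrality (0.693 + difference) / (SD × √(2/108)) gives PT 97.0%, FHA 100% and PRN 88.3% (SAP: 97.0%, 100%, 88.2%). For proportions, Φ(0.1/√(2p(1−p)/108) − 1.96) at p = 0.95 gives 92.1%, as in the SAP.

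**Pooling B and C only.** SD = √(s² + d²/4), with d the planned difference. PT: √(0.8759² + 0.234²/4) = 0.884 against 0.876. PRN: 1.437 against 1.436. This is the benign case.

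**Pooling all three arms.** With equal arms and equal within-arm SDs, Group A lower by D on the log scale, and the small B–C difference ignored, the variance of the arm means is (2/9)D². Pooled SD = √(s² + (2/9)D²). The added variance is 0.107 at 2-fold (D = ln 2), 0.576 at 5-fold and 1.178 at 10-fold. For PRN at 5-fold: √(2.063 + 0.576) = 1.624.

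| | Planned | 2-fold | 5-fold | 10-fold |
|---|---|---|---|---|
| PRN SD | 1.436 | 1.473 | 1.624 | 1.800 |
| PRN apparent power | 88% | 87% | 80% | 71% |
| PRN evaluable n per arm, 90% | 115 | 121 | 147 | 180 |
| PT SD | 0.876 | 0.935 | 1.159 | 1.395 |
| PT apparent power | 97% | 95% | 83% | 67% |

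FHA stays at or above 95% throughout.

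**Proportions.** Pooled p = (pA + 2 × 0.95)/3; n = 2p(1−p)(1.96 + 1.2816)²/0.01.

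| Group A proportion | Pooled p | Apparent power | Evaluable n per arm, 90% |
|---|---|---|---|
| 0.95 | 0.950 | 92% | 100 |
| 0.90 | 0.933 | 84% | 131 |
| 0.85 | 0.917 | 76% | 161 |
| 0.80 | 0.900 | 69% | 190 |

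At the planning values PRN sets the requirement (115, against 100 for diphtheria/tetanus and 78 for PT). With Group A at 0.90 or lower, the pooled diphtheria/tetanus figure would overtake 115.

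**Reversal.** If Group A's SD is half that of the other arms, the mean within-arm variance is s²(2 + 0.25)/3. For PRN at 2-fold: √(2.063 × 0.75 + 0.107) = 1.286. Apparent power is then about 94% when the truth is 88%.

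**Primary endpoint.** The S-IgA SD has the mirror-image flaw: Group C is pooled in although only A and B are tested. At the planned effect size of 0.35, with equal SDs and no change in C, the inflation is √(1 + (2/9) × 0.35²) = 1.014, about 1.4%.

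**The case against.** The recalculation may never happen, and nothing in it is mechanical. A committee judges the need for a change, looks also at data completeness and drop-out, and works to no stated power target; the 90% above is an assumption. The statement on the statistician's calculation names only the SDs, although the proportions come from the same pool.

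The separations are assumed too. Protocol 1.1 reports that BPZE1 raised serum IgG to PT, FHA and PRN in adults, and these children had an acellular primary series, usually given combined with diphtheria and tetanus. Group A may therefore lie close to the Boostrix arms. The SAP still plans about 360 subjects and omits the recalculation, so the point may be moot. Full pooling was also chosen to protect the blind on a committee that includes sponsor leadership.

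All of this stands, and it limits the size and urgency of the point. It does not make the three-arm figure an estimate of the right parameter.

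A reader might infer that the procedure will force a large, needless increase in enrolment. The documents do not support that: they give no Group A separation and no rule binding the committee, the direction of the SD error is not fixed, and quoting PT alone (78 rising to 135 at 5-fold) overlooks that PRN already needs 115. Nor do they support any inference that the trial's conclusions would be biased. The pooling leaves the margins, the final tests and the type I error untouched.

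**Conclusion.** The point holds as a should-fix defect in an optional step. Followed as written, 7.2 estimates the wrong nuisance parameters for all five key secondary tests, and no other section corrects this. Under equal within-arm SDs, the apparent loss of PRN power runs from about 1 percentage point (2-fold) to 17 (10-fold). For diphtheria/tetanus it runs from nil (Group A at 0.95) to 23 points (Group A at 0.80). These ranges rest wholly on the assumed separations. The likelier direction is an overstated need, but a smaller Group A SD can reverse it for the IgG endpoints. FHA is not a driver, and the effect on the primary endpoint's SD is minor at the planned effect size.

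**What to change.** Before any recalculation is run, amend Protocol 7.2 so that a team already provided for in Protocol Section 11 ("The administrative structure will include an unblinded biostatistics team (statisticians and programmers) and an external SMC") gives the committee summary statistics only:

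- **From B and C combined, without arm labels:** the PT, FHA and PRN SDs and the diphtheria and tetanus proportions. Include the residual SD after adjustment for baseline IgG, because SAP 8.2 tests these antigens by ANCOVA with baseline as a covariate and SAP Section 1 makes the SAP govern. The raw Day 29 SD alone would not match that analysis.
- **From A and B combined, without arm labels:** the SD of the S-IgA WCE log change.

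The cost is one paragraph and one summary table. The downside is that the unblinded team must separate out one arm's labels, and the committee sees a combined Boostrix-arm summary, including a seroprotection rate, during the trial. The B-versus-C contrast stays blinded, which preserves the blinding purpose given for full pooling. If no recalculation was or will be run, a statement to that effect closes the point.

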7.3 Analysis Sets

The safety analysis set will consist of all randomized subjects who receive study vaccine and have any safety data available. Subjects will be classified according to the actual vaccine received. The safety analysis will be done on this analysis set.

The intent-to-treat analysis set will consist of all randomized subjects. Subjects will be classified according to the randomized treatment group. Subject disposition, demographics, and medical history will be summarized on this analysis set.

The immunogenicity analysis set will consist of all subjects in the intent-to-treat analysis set who receive study vaccine, have a baseline and at least 1 post-vaccination sample (mucosal or serum immunogenicity testing, respectively) for which valid results were reported for the test being analysed, and have not received any component of a licensed pertussis vaccine in the past 3 years or through Day 85 of the study. Subjects will be classified according to the actual vaccine received. All immunogenicity analyses will be done on this analysis set. The substudy analysis set will also be based on this analysis set but including only subjects who are enrolled in the optional open-label substudy.

The per-protocol analysis set will consist of all subjects in the immunogenicity analysis set, with the following exclusions:

- Data from all available visits for subjects following the receipt of unsuitable investigational product (either via dispensed and/or assigned or delivered).
- Data from all available visits for subjects found to be ineligible at baseline per-protocol.
- Data from all available visits for subjects following the use of major immune modulators or immunosuppressants or following the receipt of blood products.
- Data from all available visits for subjects following clinically significant protocol deviations that can affect the efficacy (immunogenicity) results as determined by clinical review.
- Data from any visit that occurs substantially out of window as defined by exceeding 30 days past the visit window or the time point whereby the follow-up visit should have occurred, whichever is most restrictive. Standard visit windows are described in schedule of events (Table 13-1).

For analyses using the per-protocol analysis set, subjects will be classified according to the randomized treatment group.

The safety lead-in analysis set will consist of the first 45 subjects who are randomized to the study. Subjects will be classified according to the actual vaccine received. The first

45 subjects enrolled will be in the older age group of 11 to 17 years, inclusive. Cellular-mediated responses in this group following study vaccination will be analysed if subjects contribute a baseline sample and the required post-vaccination sample (ie, Day 8) that has at least 85% recovery following peripheral blood mononuclear cell (PBMC) procedures. Similarly, cellular-mediated immunity of the optional substudy will occur in a subset of subjects who contribute to Day 85 and Day 113 samples and have a similar recovery of PBMCs.

7.4 Statistical Analysis Methodology

Statistical analysis will be performed using SAS software Version 9.3 or later. Continuous variables will be summarized using the mean, standard deviation, median, first quartile, third quartile, minimum value, and maximum value. Categorical variables will be summarized using frequency counts and percentages, as well as a two-sided 95% confidence interval (CI) for proportions computed using the Agresti-Coull method when appropriate. Data will be listed in data listings.

Immunogenicity endpoints (seroconversion, GMT, and GMFR) will be summarized by baseline negative and positive status (by quantiles) of each anti-pertussis antibody (WCE, PT, FHA, PRN, and any additional anti-pertussis antibodies) and by antibody type (eg, S-IgA, IgA, and IgG separately), by the 2 age groups (6 to 10 years and 11 to 17 years, inclusive) and across age groups. Substudy analyses will assess immunity at baseline and Days 85 and 113 (independently for substudy subjects) and relative to colonization status (colonized/non-colonized) at either Day 92 or Day 99 following re-vaccination/attenuated challenge at Day 85. The mucosal and serum immunogenicity endpoints will be summarized by treatment group and by day (all subjects), including a separate analysis after Day 85 for the open-label substudy. Analyses will include the GMFs with 95% CIs and GMFRs with 95% CIs. The 95% CIs will also be provided for mucosal and serum seroconversion. For immunogenicity analysis, it is assumed that the natural log of the data is normally distributed. All statistical tests will be two-sided at 0.05 significance level.

There are 2 primary comparisons that will be tested at a two-sided significance level of 0.05. The study is considered a success if both primary comparisons meet statistical significance. The Holm procedure (also known as a stepdown Bonferroni procedure) will be used to control for multiplicity when evaluating the key secondary endpoints.

Further details of the planned statistical analyses, methods, and data conventions will be described in the SAP.

